6.1 Phase 1 Portion of the Study

The dose escalation phase of the study will employ the modified toxicity probability interval (mTPI) method in decision making concerning mocetinostat dose escalation ([Appendix 3](#)).

The mocetinostat dose levels planned for evaluation include 50, 70, and 90 mg TIW, depending on safety observations. In addition, if necessary, dose de-escalation of mocetinostat to 40 mg TIW may be undertaken.

Assessments	Screen/ Baseline	7-Day Mocetinostat Lead-In Period	Mocetinostat + Durvalumab					End of Treatment ¹⁵	
			Cycle 1		Cycle 2 and 3		≥Cycle 4		
	Within 28 days	Day 1	Day 1	Day 15 (± 2 days)	Day 1 (± 2 days)	Day 15 (± 2 days)	Day 1 (± 2 days)	End of Treatment/ Withdrawal	Post Treatment Follow Up
Coagulation ^{6,7}	X		As clinically indicated						
Urinalysis ^{6,7}	X		X		X		X		
Liver Enzyme Panel ^{6,7}	X	X	X	X	X	X	X		
Serum Chemistry ^{6,7}	X	X	X	X	X	X	X	X	
Thyroid Function Test ^{6,7}	X		X		X		X		
Blood for Pharmacokinetics ⁸			See Table 2					90 Days	
Blood for Anti-Drug Antibody ⁹			See Table 2					90 Days	
Biopsy of tumor for Biomarker Studies ¹⁰	X		X					X	
Blood Samples for Biomarker Studies ¹¹	X	X	X	X ¹¹	11				
Single 12-Lead ECG ¹²	X				Cycle 3		X	X	
TriPLICATE 12-Lead ECG ¹²		X, See Table 2	X		Cycle 2				
Echocardiogram	X			X	X		X	X	

6.1.1 Definition of Dose Limiting Toxicity

The National Cancer Institute Common Toxicity Criteria for Adverse Events (NCI CTCAE) version 4.03 will be used throughout this study. The definition of DLT includes any of the following events considered to be causally related to treatment with mocetinostat in combination with durvalumab:

- Any grade 4 immune-related adverse event (irAE is defined in [Section 8](#))
- Grade 3 or greater colitis
- Grade 3 or greater noninfectious pneumonitis irrespective of duration
- Grade 2 pneumonitis that does not resolve to ≤ Grade 1 within 3 days of the initiation of maximal supportive care
- Grade 3 irAE (excluding colitis or pneumonitis) that:
 - Does not downgrade to Grade 2 within 3 days after onset of the event despite optimal medical management including systemic corticosteroids, or
 - Does not downgrade to ≤ Grade 1 or baseline within 14 days
- Liver transaminase elevation > 8 × upper limit of normal (ULN) or total bilirubin > 5 × ULN
- Grade 3 or greater non-irAE, except for the exclusions listed below:

Sponsor: Mirati Therapeutics, Inc.

Protocol no: 0103-020

- Nausea, vomiting, anorexia, dehydration, or diarrhea that can be managed with typical medical interventions.

The definition of DLT excludes the following conditions:

- Grade 3 fatigue lasting ≤ 7 days
- Grade 3 endocrine disorder (thyroid, pituitary, and/or adrenal insufficiency) that is managed with or without systemic corticosteroid therapy and/or hormone replacement therapy and the patient is asymptomatic
- Grade 3 inflammatory reaction attributed to a local antitumor response (e.g., inflammatory reaction at sites of metastatic disease, lymph nodes, etc)
- Concurrent vitiligo or alopecia of any grade
- Grade 3 infusion-related reaction (first occurrence and in the absence of steroid prophylaxis) that resolves within 6 hours with appropriate clinical management
- Grade 3 or 4 neutropenia that is not associated with fever or systemic infection that improves by at least 1 grade within 3 days. Grade 3 or 4 febrile neutropenia will be a DLT regardless of duration or reversibility
- Grade 3 or 4 lymphopenia
- Grade 3 thrombocytopenia that is not associated with clinically significant bleeding that requires medical intervention, and improves by at least 1 grade within 3 days
- Isolated Grade 3 electrolyte abnormalities that are not associated with clinical signs or symptoms and are reversed with appropriate maximal medical intervention within 3 days.

Note that the DLT evaluation period does not include the 7 day run in of mocetinostat.

6.1.2 Dose Escalation Plan

The first cohort of patients to be enrolled will begin with the mocetinostat 7-Day Lead-In Period, receiving 50 mg on 3 days (e.g., Monday, Wednesday and Friday) and will continue into the combination regimen, with 50 mg mocetinostat administered TIW and 1500 mg durvalumab administered Q4W.

For a patient within a dose cohort to be considered evaluable for the dose-escalation decision, the patient must have either been on study for 1 full cycle and have received treatment with durvalumab and at least 9 of 12 scheduled mocetinostat doses (75%) in Cycle 1 or have experienced a DLT in Cycle 1.

Decision making rules for cohort expansion and dose escalation or de-escalation based on the experience of patients treat at a dose level are presented in [Appendix 3](#).

To ensure sufficient patient experience at the dose selected as the RP2D, enrollment at any dose level under consideration may be expanded to include at least 6 patients.

6.1.3 Definition of Maximum Tolerated Dose

The maximum tolerated dose (MTD) is defined as the highest mocetinostat dose administered in the combination regimen associated with the decision to “stay with the current dose” as determined from the Dose-Finding Spreadsheet ([Appendix 3](#)) using the experience of at least 6 patients during the first 28-day treatment cycle.

6.1.4 Definition of Recommended Phase 2 Dose

The RP2D will be the highest dose of mocetinostat evaluated that is associated with:

Sponsor: Mirati Therapeutics, Inc.

Protocol no: 0103-020

- Sufficient safety/tolerability to anticipate that patients will typically be able to receive treatment with at least 75% of the intended dose intensity of mocetinostat and 100% dose intensity of durvalumab; and
- No observed \geq Grade 3 or serious irAEs causally related to the combination regimen.

A dose level below the MTD may be selected as the RP2D.

6.2 Phase 2 Portion of the Study

The Phase 2 portion of the study will enroll patients with NSCLC into one of the following 4 population cohorts:

- Cohort 1 – Patients naïve to treatment with immunotherapy, having tumor with no/low PD-L1 expression
- Cohort 2 – Patients naïve to treatment with immunotherapy, having tumor with high PD-L1 expression
- Cohort 3 – Patients previously treated with an anti-PD-L1 or anti-programmed cell death 1 (PD-1) agent with clinical benefit response followed by progression of disease
- Cohort 4 – Patients previously treated with an anti-PD-L1 or anti-PD-1 agent with progression of disease \leq 16 weeks after initiation of treatment.

Tumor PD-L1 expression will be determined by the PD-L1 (SP263) CDx assay. No/low PD-L1 expression is defined as positivity $<25\%$ of tumor cells; high PD-L1 expression is defined as positivity $\geq 25\%$ of tumor cells. Tumor samples used to establish PD-L1 expression for eligibility must have been collected after the most recent systemic therapy.

The sample sizes for the populations to be enrolled in the Phase 2 portion of the study are based on Predictive Probability Design, which allows for flexibility in the number of patients to be included at each stage in order to ensure that sufficient number of evaluable patients are available for decision to continue or to stop enrollment of additional patients.

- Cohorts 1, 3 and 4: Stage 1 of enrollment will include a minimum of 9 evaluable patients. With exactly 9 evaluable patients at Stage 1, if at least 1 patient has an Objective Response, 8 additional evaluable patients will be enrolled, for a total sample size of 17 evaluable patients. If at least 3 objective responses are observed, further investigation may be warranted.
- Cohort 2: Stage 1 of enrollment will include approximately 17 evaluable patients. With exactly 17 evaluable patients at Stage 1, if at least 5 patients have Objective Responses, 27 additional evaluable patients will be enrolled, for a total sample size of 44 evaluable patients. If at least 18 Objective Responses are observed, further investigation may be warranted.

The exact stopping rules for all cohorts will be calculated based on the Predictive Probability Design, once the exact number of patients evaluable at Stage 1 is known. The aim is to get a minimum of 9 evaluable patients at Stage 1 for cohorts 1, 3 and 4 and about 17 evaluable patients at Stage 1 for cohort 2.

The populations included in Cohorts 3 and 4, who have had disease progression during treatment with a checkpoint inhibitor, represent a potential unmet medical need. For this reason, if results in Stage 2 of enrollment are of high interest, enrollment may be expanded to as many as 100 patients total in each cohort to narrow the 95% confidence interval (CI) around the ORR point estimate and more fully characterize the secondary endpoints in the population of interest.

In order to be part of the clinical activity evaluable population, the patient must have at least one on-study disease assessment or discontinue from treatment for PD prior to this assessment. Patients who

Sponsor: Mirati Therapeutics, Inc.

Protocol no: 0103-020

discontinue treatment prior to the first on-study disease assessment for an AE, toxicity, or withdraw consent are considered non-evaluable for disease assessment. These patients will not be part of the clinical activity evaluable population.

Disease response and progression as documented by the investigator in the CRF will be the basis for patient management and study expansion decision making. Unconfirmed objective responses recorded in the CRF may be used as an initial basis for expansion of study enrollment; however, follow-up evaluations on patients with unconfirmed responses must continue to support the decision to continue to the full number of patients to be included in the next stage. Central radiology review for disease response and progression may be added to the study during Stage 2. If this occurs, central review of all radiologic assessments performed in the study will be expected (including retrospective review of patients enrolled in Stage 1), and central radiology review for disease response will be the basis for the primary statistical analyses to estimate the ORR and its confidence interval, as well as the DR and PFS.

Study treatment will continue until disease progression, unacceptable AEs, patient refusal, or death.

6.3 Sample Size Considerations

6.3.1 Phase 1

Approximately 24 patients may be enrolled into the Phase 1 portion of the study. A precise sample size cannot be defined, as it is dependent on the number of dose escalations based on the mTPI method.

The mTPI method ([Ji 2013](#)) will be employed in decision making concerning dose escalation within each regimen investigated. The assumptions to be applied in establishing the mTPI methodology are:

- Each specific regimen exploration will include up to 30 patients
- The MTD is defined to have 0.25 probability of toxicity; and
- The acceptable variance around the MTD is ± 0.05 (i.e., the region of the MTD is 20% to 30% incidence of DLT).

6.3.2 Phase 2

Up to 261 patients may be enrolled into the Phase 2 portion of the study.

The 4-cohort Phase 2 portion uses sample sizes based on Predictive Probability Design (Lee-2008). ORR in accordance with RECIST 1.1 is the primary clinical benefit endpoint. In creating the statistical designs, the Type 1 error (α) is constrained to <0.05 and Power ($1-\beta$) is constrained to ≥ 0.90 .

6.3.3 Statistical Design Applied to Phase 2 Cohorts 1, 3 and 4

The ORR using a PD-L1 inhibitor in the population with advanced NSCLC having no or low PD-L1 expression, or prior disease progression on a checkpoint inhibitor, is assumed to be 5% (p_0); thus this rate is considered uninteresting. The target ORR using mocetinostat in combination with durvalumab in this study is 30% (p_1). Stage 1 of enrollment will include a minimum of 9 evaluable patients per cohort. With exactly 9 evaluable patients at Stage 1, if at least 1 patient has an Objective Response, 8 additional evaluable patients will be enrolled, for a total sample size of 17 evaluable patients. If at least 3 Objective Responses are observed, further investigation may be warranted. If the true ORR is 5% (null hypothesis), the probability of early termination during the study is 0.63; the Type 1 error is equal to 0.0466 and the power is equal to 0.9045.

Sponsor: Mirati Therapeutics, Inc.

Protocol no: 0103-020

6.3.4 Statistical Design Applied to Phase 2 Cohort 2

The ORR using a PD-L1 inhibitor in the population with advanced NSCLC having high PD-L1 expression is assumed to be 27% (p_0); thus this rate is considered uninteresting. The target ORR using mocetinostat in combination with durvalumab in this study is 50% (p_1). Stage 1 of enrollment will include approximately 17 evaluable patients. With exactly 17 evaluable patients at Stage 1, if at least 5 patients have Objective Responses, 27 additional evaluable patients will be enrolled, for a total sample size of 44 evaluable patients. If at least 18 Objective Responses are observed, further investigation may be warranted. If the true ORR is 27% (null hypothesis), the probability of early termination during the study is 0.50; the Type 1 error is equal to 0.0303 and the power is equal to 0.9018.

The exact stopping rules for all cohorts will be calculated based on the Predictive Probability Design, once the exact number of patients evaluable at Stage 1 is known. The aim is to get about 9 evaluable patients at Stage 1 for cohorts 1, 3 and 4 and about 17 evaluable patients at Stage 1 for cohort 2.

If Stage 2 results in Cohorts 3 and 4 are of high interest for efficacy (as decided by the sponsor), enrollment may be expanded to as many as 100 patients total in each cohort to narrow the 95% Confidence Interval (CI) around the ORR point estimate.

6.4 Randomization

There is no randomization for the study.

7.0 Analysis Populations

7.1 Enrolled Population

The enrolled population is defined as all patients who sign an informed consent for the study. Disposition summaries will be displayed using the enrolled population.

7.2 Modified Intent-to-Treat Population

The Modified Intent-to-Treat (mITT) population is defined as all patients who receive treatment with both mocetinostat and durvalumab on this study.

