## 9.3 Analysis Populations

### 9.3.1 *Modified Intent-to-Treat Population*

The Modified Intent-to-Treat (mITT) population is defined as all patients who receive treatment with both mocetinostat and durvalumab on this study.

The primary efficacy analyses of the primary and secondary efficacy endpoints will be performed in the mITT population. In addition, the mITT population will be used in making decisions to expand the study to the next stage of enrollment (to up to 100 patients).

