#### **9.4.4 Progression Free Survival**

Progression-free survival (PFS) is defined as the time from date of first study treatment to first PD or death due to any cause in the absence of documented PD. Censoring for the PFS endpoint will be assigned on the date of the last tumor assessment if no assessment of tumor progression is identified and the patient does not die while on study. For patients in whom two or more sequential assessments are missed, followed by the finding of tumor progression, the PFS endpoint will be censored on the date of the last tumor assessment before the gap. Patients lacking an evaluation of disease after first study treatment will have their PFS time censored on the date of first dose with duration of 1 day. Patients who start a new anti-cancer therapy prior to documented PD will have the endpoint censored at the date of the last tumor assessment prior to the start of the new therapy. The Kaplan-Meier method will be used to obtain the estimate of median progression-free survival time.

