6.0 Study Design

This is an open-label Phase 1/2 evaluation of mocetinostat in combination with durvalumab. The Phase 1 segment will define the RP2D of mocetinostat to be used in combination with full dose regimen of durvalumab; eligible patients will have an advanced solid tumor disease that is not amendable to curative treatment. The Phase 2 segment will evaluate the clinical activity of mocetinostat in combination with durvalumab, as assessed by ORR in accordance with Response Evaluation Criteria in Solid Tumors (RECIST) version 1.1, in patients with locally advanced, unresectable or metastatic NSCLC who have previously received at least one platinum-containing doublet chemotherapy regimen for advanced disease. Patients who have previously received treatment with checkpoint inhibitors may be enrolled in the Phase 1 assessment and will be enrolled into dedicated cohorts in the Phase 2 assessment. Secondary objectives include secondary efficacy endpoints, PK, incidences of ADA and change in tumor PD-L1 expression.

The schedule of assessments to be performed in the study is presented in [Table 1](#). Triplicate electrocardiogram (ECG) assessments, PK, and ADA collection time points are presented in [Table 2](#).

The treatment regimen to be evaluated in this study includes a 7-Day Lead-In Period of mocetinostat single agent administered three times weekly (TIW; e.g., Monday, Wednesday and Friday) followed by administration of the combination regimen with durvalumab. The RP2D dose of mocetinostat will be established in successive dose escalation cohorts in the Phase 1 portion of the study and utilized in the Phase 2 portion of the study. The dose and regimen of durvalumab to be used throughout the study is 1500 mg on Day 1 of each 28-day cycle (i.e., Q4W).

Sponsor: Mirati Therapeutics, Inc.

Protocol no: 0103-020

Table 1: Schedule of Assessments

The Schedule of Assessments provides an overview of the protocol visits and procedures. Refer to Section **Error! Reference source not found.** for detailed information on each assessment. Additional, unplanned assessments should be performed as clinically indicated, including for the purpose of fully evaluating adverse events.

Assessments	Screen/ Baseline	7-Day Mocetinostat Lead-In Period	Mocetinostat + Durvalumab				End of Treatment ¹⁵		
			Cycle 1		Cycle 2 and 3				

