8.1.5 Overall Survival (OS)

OS is defined as the time from first dose of study drug to the date of death due to any cause. OS (in months) is calculated as (date of death – date of first dose of study drug +1)/30.4. For patients who are continuing study at the time of an analysis, lost to follow-up or who withdraw consent, the OS endpoint will be censored on the last date that patients were known to be alive. The date last known to be alive is derived from the CRF and may include the latest Visit date for patients on-going study or the latest Date of Contact on the Long-Term Follow-Up/Survival Status page, whichever occurs latest. For patients with no follow-up after first dose of study drug, OS will be censored at the date of first dose.

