8.1.6 Progression-Free Survival (PFS)

PFS is defined as the time from the first dose of study drug to the date of PD or death due to any cause, whichever occurs first. PFS (in months) will be calculated as (first event date – first dose date +1)/30.4.

Censoring rules will be applied to PFS:

Sponsor: Mirati Therapeutics, Inc.

Protocol no: 0103-020

- Patients lacking evaluation of disease after first study treatment will have their PFS time censored on the date of first dose with duration of 1 day unless they die within 2 tumor assessments of baseline, then they will be treated as an event with date of death as the event date.
- Patients with baseline or post-baseline assessments inadequate to apply RECIST criteria will have their event time censored on the date of the first dose of study drug.
- Event time will be censored on the date of the last evaluable assessment documenting absence of PD for:
 - Patients on-study and progression-free at the time of an analysis;
 - Patients who have PD or death on study after ≥ 2 consecutive missed tumor assessments (i.e., >12 weeks + 14 days after the last on-study disease assessment);
 - Patients given alternative cancer treatment prior to PD or death on-study.
- Patients who die on-study after ≥ 2 consecutive missed tumor assessments (i.e., >12 weeks + 14 days after the last on-study disease assessment) will have their event time censored on the date of the last evaluable assessment documenting absence of PD.

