12.5.2 Time-to-event Variables

Time-to-event variables, DR, PFS, and OS, will be summarized by phase and by dose level/cohort and overall within each phase, descriptively using the Kaplan-Meier estimate (SAS® PROC LIFETEST). The median, 25th percentile, and 75th percentile of DR, PFS, and OS and their two sided 95% CIs using the complementary log-log transformation method ([Collett, 1994](#)) will be calculated where appropriate. In addition, minimum and maximum will also be displayed. Kaplan-Meier plots will be provided for DR, PFS, and OS.

Sponsor: Mirati Therapeutics, Inc.

Protocol no: 0103-020

DR, PFS, and CBR will be based on the Response Assessments by the Investigator. DR will be conducted in both the clinical activity evaluable and mITT populations. PFS and OS will be conducted in the mITT population.

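### PFS and OS start at the mocetinostat lead-in but are analysed only in patients who go on to receive durvalumab, so the lead-in week is guaranteed survival time and patients lost before durvalumab are left out

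*SAP*

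**What the plan says.** **Who is analysed.** SAP 7.2: "The Modified Intent-to-Treat (mITT) population is defined as all patients who receive treatment with both mocetinostat and durvalumab on this study". Protocol 9.3.1 uses the same definition. SAP 12.5.2 adds: "PFS and OS will be conducted in the mITT population". It plans no all-treated or landmark version of either endpoint.

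**When durvalumab starts.** SAP 6.0: "The treatment regimen to be evaluated in this study includes a 7-Day Lead-In Period of mocetinostat single agent". Durvalumab is first given on Cycle 1 Day 1, after the lead-in.

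**When the clock starts.** SAP 8.1.6: "PFS is defined as the time from the first dose of study drug to the date of PD or death due to any cause". SAP 8.1.5: "OS is defined as the time from first dose of study drug to the date of death due to any cause". Protocol 9.4.4 agrees: "Progression-free survival (PFS) is defined as the time from date of first study treatment to first PD or death due to any cause". SAP 9.3 takes study treatment to mean either drug or both, and exclusion criterion 3 in Protocol 4.2 identifies the first study treatment dose with the lead-in. Time zero is therefore Lead-In Day 1.

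**Other sets.** The Safety population (SAP 7.4) needs one dose of either drug. The clinical activity evaluable population (SAP 7.3) needs an on-study disease assessment or a stop for PD, and does not require durvalumab. SAP 12.5.1 makes the evaluable set primary for ORR and mITT supportive, whereas Protocol 9.3.1 makes mITT primary for all efficacy endpoints.

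**The concern.** Entry to the analysis set depends on something that happens about a week after time zero. No mITT patient can die before the first durvalumab dose, yet those days count as survival time (immortal time). Patients who start the regimen and never reach durvalumab are removed from the survival analyses.

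The early-death rule in SAP 8.1.6 and the rule in SAP 12.5.1 that unassessable patients are non-responders act only within the analysed set, so they do not bring these patients back. A patient who stops for toxicity or withdraws consent in the lead-in, before any scan, is also outside the evaluable set and so is in no efficacy analysis.

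The lead-in is part of the regimen under evaluation. With no control arm, a bias of this kind cannot cancel. At stake is modest optimism in PFS, OS, 1-year survival and the mITT ORR.

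**Working it through.** **1. The plan's own figures.** The documents set no numerical target for PFS or OS. The stated design figures concern ORR, and they reproduce with the exact two-stage binomial: the sum over x ≥ a of P(X1 = x) × P(X2 ≥ r − x), where a is the Stage 1 minimum and r the final minimum number of responses.
- Cohorts 1, 3 and 4 (at least 1 of 9, then at least 3 of 17; 5% against 30%): early termination 0.95^9 = 0.630, Type 1 error 0.0466, power 0.9045.
- Cohort 2 (at least 5 of 17, then at least 18 of 44; 27% against 50%): early termination 0.498, Type 1 error 0.0303, power 0.9018.

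All match, and none depends on this point.

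**2. Guaranteed time.** With durvalumab on study day 8, 7 days precede it: 7/30.4 = 0.23 months. The shortest OS possible in mITT is a death on day 8: 8/30.4 = 0.26 months by the SAP formula.

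**3. Deaths expected in that week.** Assume exponential survival with a 12.0-month median (the pembrolizumab OS figure in Protocol 1.1.1, for scale only). The share dying in 7 days is 1 − 2^(−0.23/12) = 1.3%, or 0.2 of 17 patients and 1.3 of 100. For medians from 6 to 18 months it is 2.6% to 0.9%.

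**4. Effect on OS.** Under the same model, median OS is 12.0 + 0.23 = 12.23 months in mITT against 12.00 when lead-in deaths are included. One-year survival is 50.7% against 50.0%.

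**5. Effect on PFS.** Take 3.7 months as the median (same source, for scale only).
- Upper illustration: if PFS events occurred in the lead-in at their usual rate and were all excluded, the median would be 3.93 against 3.70 months.
- More realistic: scans run every 8 weeks from Cycle 1 Day 1, so in practice only deaths are excluded. Restoring the 1.3% moves the median by 3.7 × log2(1 − 0.013) = −0.07 months, about 2 days.

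**6. Selection.** Let q be the share of starters who never receive durvalumab. The documents give no value, so 2% to 15% is assumed. If every such patient died at once (a worst case), the all-treated median OS solves (1 − q) × S(t) = 0.5, where S is the mITT curve:

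| q | Median OS, all treated (months) | Median OS, mITT (months) |
|---|---|---|
| 2% | 11.88 | 12.23 |
| 5% | 11.34 | 12.23 |
| 10% | 10.41 | 12.23 |
| 15% | 9.42 | 12.23 |

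**7. mITT ORR.** Three responders in 17 is 17.6%. Counting 1 to 3 patients lost before durvalumab gives 3/18 = 16.7% to 3/20 = 15.0%.

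**The case against.** The strongest reply is that the effect is small, visible and inconsequential for decisions. Most of this stands.

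- PFS and OS are secondary, summarised by Kaplan-Meier and not tested.
- Entry requires ECOG 0 or 1 and adequate organ function, so few deaths in one week are to be expected.
- The objective concerns the combination, so a two-drug set is a recognisable choice. That does not justify starting its clock before the second drug.

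A reader might infer more than the documents support:

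- *All early failures disappear from the trial.* Only patients who never receive durvalumab are dropped. A patient with a lead-in adverse event who then receives it stays in mITT. Those dropped remain in the Safety population, in disposition with reasons (SAP 12.1), and in the death and survival listings (SAP 12.6.2 and 12.6.15).
- *PFS is inflated by 6% (0.23/3.7) or more.* That needs progression to be recorded in a week with no scheduled scan, and Protocol Appendix 5 does not accept clinical deterioration alone as PD.
- *The primary ORR is biased.* Under the SAP, the primary set does not require durvalumab and keeps lead-in stops for PD as non-responders. Only under the wording of Protocol 9.3.1 would the primary ORR be affected, and that conflict is a separate matter.
- *Survival is overstated by several percentage points, most of all in Cohort 4.* This rests on loss rates that the documents do not give. Cohort 4 patients did progress early on a checkpoint inhibitor, but nothing shows that they fail within a 7-day lead-in.

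**Conclusion.** The mismatch is real. The mITT definition, the time origin and the choice of mITT as the only set for PFS and OS together guarantee at least 0.23 months of survival and exclude patients lost before durvalumab. The guarantee is strict for death and only practical for progression.

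The bias is upward and probably small: about 0.2 months in median OS and 0.7 percentage points in 1-year survival under an exponential model with a 12-month median, and about 2 days in median PFS. Selection could add more, in proportion to an unknown number lost. The table above is a worst case on assumed rates, not an estimate. Stage decisions based on the evaluable set, and the design's error rates, do not depend on this point. It is worth correcting because the plan already holds the population and follow-up needed.

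**What to change.** In SAP 12.5.2, and to match in Protocol 9.3.1:

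1. Analyse PFS, OS and 1-year survival in all Phase 2 patients with at least one dose of study drug (the existing Safety population definition), with the clock at first dose.
2. If the two-drug mITT set is kept for supportive tables, start its PFS and OS clock at the first durvalumab dose.
3. Count patients who never receive durvalumab as non-responders in a supportive all-treated ORR.
4. Report the number of patients lost before durvalumab, with reasons.

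The existing censoring rules in SAP 8.1.6 then apply. Lead-in deaths become PFS events. A patient who stops for toxicity with no later scan is censored at Day 1 for PFS, unless death follows within the period that rule allows, but still contributes to OS. The change therefore repairs OS fully and PFS mainly for deaths.

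The cost is a few sentences and one extra count. No new data are needed, since survival is already followed after treatment stops. The downside is that reported survival and supportive ORR may be slightly lower.
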